We undertook a full literature review of HRQoL following emergency admissions for each of the five conditions. The main finding was that for some but not all of these conditions appropriate HRQoL were available from the literature. For example, for patients that present with an emergency appendicitis, appropriate measure of HRQoL (EuroQoL, EQ-5D) for the year after the index emergency admission will be available from the CODA trial²³. For, other conditions our initial review suggests that appropriate HRQoL may not be available directly from the literature.

We therefore also propose a complimentary appropriate to estimating HRQoL for those conditions without appropriate literature-based utility values. We will use a published 'EQ-5D 'utility calculator' that can provide appropriate EQ-5D (HRQoL) scores for patients in the UK according to the

diagnostic categories (ICD10), age, and gender of the individual patients included in our study from the HES dataset⁵⁵. While this approach has been extensively used in previous cost-utilities studies, we will carefully check the plausibility of the HRQoL estimates for the conditions in our study. This 'sense check' will take two forms: first, for those conditions such as cholelithiasis where there are already published HRQoL values we have cross-compared the values across the two alternative sources, and found that they are similar^{52,56}. Second, we will present the HRQoL from the EQ-5D calculator to the clinical and PPI panels, as a further check of the 'face validity' of the estimates.

Finally, QALYs will be calculated using the 'area under the curve' approach by combining the most appropriate HRQoL utility score (base case) with the data available from HES/ONS on each individual patient's survival. To examine the robustness of the findings to the choice of HRQoL, we will undertake sensitivity analysis by using alternative but also plausible estimates of HRQoL from the literature, or taking the approach adopted by Meacock et al⁵⁷ for estimating QALY for health service evaluations that use HES data when no relevant HRQoL data are available from the literature.

(see separate PPI section).

We will then report quality-adjusted life years (QALYs) up to one year by combining survival time with QoL estimates using the 'area under the curve' approach⁵⁸.

Analysis

We will estimate the relative costs and cost-effectiveness of emergency surgery (operative) versus comparator strategies for each acute condition according to broad ICD-10 diagnostic categories. We will report incremental costs per life year and per QALY gained. The main cost-effectiveness metric will be the incremental net monetary benefit, which will be calculated by valuing QALYs by the NICE recommended thresholds of £20,000 and £30,000 per QALY, and then subtracting the incremental cost⁴⁵. In the base case analysis, we will use 3 stage least-squares (3SLS) regression approaches that we have developed for IV designs that allow for the correlation between the costs and QALYs while estimating cost-effectiveness⁵⁹.

We will undertake extensive sensitivity analyses to test whether conclusions are robust to key assumptions. We will consider the impact of taking a hospital versus PSS perspective, to using different sources for the HRQoL and unit cost data, to alternative assumptions about the distribution of the cost data (e.g. gamma or log normal distribution) and to taking a longer time horizon (lifetime vs one year). To estimate lifetime cost-effectiveness, we will access use all HES-ONS linked mortality and resource use data subsequent to the index admission (up to March 2018), which will provide up to 10 years follow-up data. The long-term modelling will extrapolate from these observed data by fitting alternative parametric survival curves (e.g. Weibull, exponential, lognormal, log logistic and Gompertz). We will choose the extrapolation approach that gives the most plausible predictions of long-term survival⁶⁰.

Outputs

We will report the relative cost-effectiveness of emergency surgery versus comparator strategies for these five common acute conditions.

Objective 3

Design

We will estimate the relative effectiveness and cost-effectiveness of emergency surgery, according to patient subgroup. We will recognise that effectiveness and cost-effectiveness may differ according to observed and unobserved patient- and service-level characteristics. We will predict counterfactual outcomes following both emergency surgery (operative care) and the comparator for each patient using the local-IV (LIV) approach developed by Basu^{2,61,62}. We will generate individual-level

estimates of effectiveness and cost-effectiveness. We will aggregate these individual-level estimates to report relative effectiveness and cost-effectiveness according to relevant subgroups defined by risk factors such as refined diagnostic group, age, ethnicity, index of multiple deprivation, co-morbidities, past medical history, admission route. We will report results according to each risk factor alone and then in combination.

The LIV approach will estimate person-centered average treatment (PeT) effects allowing for confounding, but will also recognise that the effects of emergency surgery are likely to be heterogeneous according to the patients' characteristics^{2,61-63}. We will identify "marginal" patients for whom the physician is in equipoise about the decision for surgery according to both those prognostic characteristics that are measured in HES (e.g. age, comorbidity, diagnosis), and those that are unmeasured (e.g. illness severity). For these "marginal patients" a small change (or nudge) in the TTO can determine whether they receive surgery, but will not change the distribution of their risk factors. That is, at the time of emergency admission, Patients A and B may be at similar overall risk of death, but Patient A may be admitted to a hospital with a slightly higher TTO, and is more likely to have an operative procedure than Patient B.

By comparing outcomes for two groups of patients defined according to small differences in the TTO (the IV), but with similar risk profiles, we will therefore provide estimates of the causal effect of emergency surgery for marginal patients. By repeating this contrast across different levels of the TTO, we will estimate the required treatment effects for sets of marginal patients with different characteristics. The person-level effects of emergency surgery will then be estimated by averaging the effects for those marginal patients who share the same observed characteristics. The LIV approach will exploit information about the choice of surgery for each individual according to their observed characteristics, and this relationship between the choice and the observed risk factors will be informative about the level of each patients unobserved characteristics.

Analysis

First, we will estimate each patient's propensity for emergency surgery according to their observed characteristics and the hospital TTO using a probit model. Second, we will estimate the relationship of the observed patient characteristics and their propensity for emergency surgery with each outcome. The effects of emergency surgery on binary outcomes will be estimated using probit models, count outcomes with Poisson models, and continuous outcomes with generalised linear models. From these regression models we will estimate the effect of a change in the propensity for emergency surgery on each outcome, that is the causal effects of surgery for marginal patients providing PeT effects estimates for each patient.

The resultant PeT effects can be interpreted for each patient as the difference in their predicted outcomes with versus without emergency surgery. These person-level treatment effects will be aggregated to report the effectiveness and cost-effectiveness of emergency surgery for each of the five conditions, and for each pre-specified subgroup of interest, for example to age, gender, ethnicity, number of co-morbidities and route of hospital admission (accident and emergency, GP or elsewhere in hospital). The effectiveness of emergency surgery versus the comparator will be reported as mean (95% CI) differences in mortality, readmissions, costs, QALYs and incremental net monetary benefits.

Finally, we will develop predictive models (logistic regression) to examine which risk factors alone or in combination, predict which subgroups emergency surgery is relatively effective or cost-effective for based on the patients' PeT effects. We will define the clinical benefit of interest as a 10% difference in one-year mortality, and the metric of cost-effectiveness as a positive incremental net benefit. All standard errors will be calculated with non-parametric bootstrapping, and will account for clustering of individuals within hospitals.

To assess whether findings are robust to the choice of LIV model, we will consider alternative statistical models including: different functional forms; the inclusion versus exclusion of higher order

terms for continuous baseline measures such as age, and interaction terms between all the covariates.

Outputs

We will report the relative effectiveness and cost-effectiveness according to policy-relevant patient subgroups including, age, gender, past medical history and route of hospital admission. We will identify subgroups where there may be cost savings from increased uptake of either operative or non-operative strategies. We will itemise those resource items where reduction in use (e.g. consumables required for operative procedures) may lead to short-term cost savings.

3. Project Outputs

We will report the relative effectiveness and cost-effectiveness according to policy-relevant patient subgroups including, age, gender, past medical history and route of hospital admission. We will identify subgroups where there may be cost savings from increased uptake of either operative or non-operative strategies. We will itemise those resource items where reduction in use (e.g. consumables required for operative procedures) may lead to short-term cost savings.

4. Dissemination, projected outputs, knowledge mobilisation

This work is driven by a significant gap in our understanding of the risks, benefits and costs of emergency surgery and it is important that our recommendations for clinical practice are fed into NHS guidelines and can be used to shape practice. The study has been designed to maximise research impact. The specific research questions directly tackle those priorities that have been designated by authoritative sources such as the GIRFT report, clinical opinion leaders, service commissioners, leaders of surgical networks and PPI representatives. These views have shaped the objectives and the choice of conditions, operative and non-operative strategies. Direct communication of knowledge to key clinical organisations, and where appropriate, input into clinical guideline development, will be ensured by team members (Royal Colleges and Association of Surgeons – [name], [name]; NHS England – [name]). This will include contributing to future RCS initiatives⁶⁴, and working with NHS Rightcare to modify decision aids aimed at supporting shared decision making⁶⁵. We will also draw on members of our advisory group who have roles in guideline development, and advising the Department of Health, and who will help ensure we exploit opportunities for maximising the impact of this research.

The research will provide recommendations to commissioners and providers of surgical services on those services where disinvestment is warranted, those where additional investment is required, and those where additional evidence, for example from new RCTs, would be of greatest value.

The research findings will be presented at high profile national and international clinical conferences (surgical, perioperative). While the study has used HES data from England, we will ensure that both the empirical and methodological insights have wide relevance. We will work with our international network of surgeons, and with our international advisory panel (see below), to consider carefully the direct implications of the findings to other countries. The methods will be discussed at academic meetings, in particular the Health Services Research network, and Health Economist study group meetings in the UK, the European Causal inference network, and the American Health economists study group meeting (USA).

The design and translation workshops will draw on the views of patient representatives, and will consider the translation of the findings into accessible and informative summaries appropriate to the audiences of interest, and effective modes of dissemination via special interest groups (see below for further details). The findings will be presented to select groups of professional stakeholders (for example NICE guidelines committees, NHS England), commissioners and managers of surgical services and those setting future research priorities. We will work closely with [name] and colleagues at the University of Pennsylvania to ensure that this work is disseminated throughout

international surgical networks, in particular through presentations at the American College of Surgeons Clinical Congress. This congress will provide an excellent opportunity to translate the implications of the findings, and the wider application of the methods to key surgical opinion leaders.

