Exclusion criteria for defining the *index admission* will include: age less than 18, a previous emergency admission for the condition within the year prior to the index admission, referrals from tertiary referral centres (see IV assumptions below), and any additional exclusion criteria deemed appropriate by the clinical panel, for example minimum surgical volume thresholds for a particular hospital.

Table 1: Exemplar acute conditions, interventions and comparator strategies, and trust-level tendency to operate (TTO), from pilot HES data (2014-5)

Acute condition ¹	Population ² (estimated cohort 09-18)	Intervention ³	Comparator ³	NHS Trust TTO ⁴ median (IQR)	F statistic ⁵
Appendicitis	333,000	Appendectomy	Supportive care; Antibiotic treatment	89.3% (84.9%, 92.8%)	114
Cholecystitis	422,000	Cholecystectomy	Delayed cholecystectomy	17.3% (11.2%, 25.0%)	65
Diverticulitis	224,000	Resection; Colectomy; Laparoscopic lavage	Antibiotic therapy; intravenous fluid therapy Percutaneous	9.0% (6.6%, 10.9%)	678

			drainage of abscess		
Acute symptomatic hernia ⁶	70,000	Repair of hernia	Watchful waiting; Delayed repair of hernia	46.7% (39.4%, 58.7%)	148
Intestinal obstruction (small or large bowel)	235,000	Adhesiolysis; Colonic stenting; Bowel resection	Watchful waiting with intravenous fluid	29.9% (25.5%, 34.3%)	931

¹Acute condition refers to pathology and ensuing complications. The clinical panel will define specific complications related to pathology for the final inclusion criteria ²Population defined by ICD-10 codes. ³Intervention and elective surgery comparators are defined by OPCS codes. ⁴Percentage of the eligible population with an intervention within index HES episode. ⁵From Cragg-Donald weak identification test. ⁶Includes inguinal hernia, femoral and incisional.

Intervention

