We will use the generalized effect ratio³⁸, that provides the same point estimates as two-stage least squares, but also correct confidence intervals³⁹. For survival outcomes, we will apply IV methods for Cox survival models^{40,41}.

We will undertake three extensive sets of sensitivity analyses. First, we will draw from the views of the clinical panel to test whether the conclusions are robust to alternative but plausible selection criteria for the subpopulations, interventions and comparators of interest (see earlier section). Second, we will assess the robustness of the major IV assumptions by reporting nonparametric bounds for the IV estimate⁴², and investigating the extent to which results are robust to the association of an unobserved confounder with both the IV and the outcome^{25,43}. We will investigate whether our results are robust to alternative statistical models by estimating results based on logistic regression models using the plug-in principle for estimation⁴⁴.

Output

We will report the relative effectiveness of emergency surgery versus comparator strategies for each of the five acute conditions, for patients presenting as emergency hospital admissions to NHS hospitals in England.

Objective 2

Design

The CEA will take a hospital and personal social services perspective (PSS)⁴⁵. In the base case, the study will report results over a one-year time horizon and incorporate patient-level resource use (HES) and mortality data (ONS), and estimates from the literature for HRQoL⁴⁶, community care costs⁴⁶, and unit costs^{47,48}.

Resource use and unit costs

The study will measure resource use items that are the major drivers of relative cost and cost-effectiveness for patients with relevant acute conditions^{49,50}. These resource use categories are: the receipt of operative and other procedures, the duration of hospital stay for the index admission, subsequent readmissions or re-interventions, and transfer to continuing care, in particular, care homes.

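### For conditions scored with the EQ-5D calculator, the planned QALY contrast carries only the survival component, because the stated utility inputs do not include treatment strategy or later events

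*Protocol*

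**What the plan says.** All references are to Protocol section 2.2.2.

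- **Which conditions.** Objective 2, Outcomes, reports that suitable utilities exist for some conditions only, and brings in a published EQ-5D calculator "for those conditions without appropriate literature-based utility values". These conditions are not listed. Appendicitis is given a trial source, and published values are said to exist for cholelithiasis.
- **Inputs to the score.** The calculator scores patients according to "diagnostic categories (ICD10), age, and gender of the individual patients included in our study from the HES dataset".
- **How the QALY is formed.** The base case works by "combining the most appropriate HRQoL utility score (base case) with the data available from HES/ONS on each individual patient's survival". The end of the subsection says again that QALYs up to one year are obtained "by combining survival time with QoL estimates using the 'area under the curve' approach". The horizon is set under Objective 2, Design: "In the base case, the study will report results over a one-year time horizon".
- **Post-index events.** Under Resource use and unit costs, the items to be costed include "subsequent readmissions or re-interventions, and transfer to continuing care, in particular, care homes". No utility decrement is attached to any of them.
- **Checks.** Calculator scores are compared with published values where these exist, and are shown to the clinical and PPI panels for face validity. Sensitivity analyses change the source of the utilities.
- **Use of the result.** Incremental net monetary benefit at £20,000 and £30,000 per QALY is the main metric (Objective 2, Analysis). Objective 3, Analysis, defines "the metric of cost-effectiveness as a positive incremental net benefit" when subgroups are classified.

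**The concern.** The two strategies can differ in quality of life without differing in mortality: recovery from an operation, a period with symptoms before a deferred one, readmission. For hernia, Table 1 gives the comparator as "Watchful waiting; Delayed repair of hernia". If utility depends only on diagnosis, age and gender, two patients who match on these and survive equally long receive the same QALYs under either strategy.

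The protocol treats the same events unevenly. Readmissions, re-interventions and delayed surgery count on the cost side of the net benefit but not on the health side. Where mortality hardly differs, the net benefit is close to minus the cost difference, and the cheaper strategy is classed as cost-effective. The planned checks ask whether the scores suit the condition. Neither they nor the change of utility source is said to test whether scores should differ by strategy. The lifetime analysis extends survival and cost but adds no such term.

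**Working it through.** The protocol gives no utility, QALY or net-benefit figure, so there is nothing to reproduce. The check is algebra, a simulation and an illustration of size.

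**1. Algebra.** Let u be the calculator score (diagnosis, age, gender), T the years alive within the one-year horizon, C the cost and λ the value of a QALY.

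- QALY = u × T.
- Treatment does not enter u, so a patient's QALY effect is u × ΔT.
- Incremental net benefit = λ × u × ΔT − ΔC.
- If ΔT = 0 for every patient, the QALY effect is 0 and the net benefit is −ΔC.

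Because u varies between patients, the average of u × ΔT is a weighted survival effect. It is not strictly one constant times the average life-year effect.

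**2. Simulation of an instrumental-variable (Wald) estimate.** Assumed inputs: 2,000,000 patients, utility depending on age and sex with mean 0.825, an unmeasured confounder, and a true utility benefit of surgery of 0.05 for the year.

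| Scenario | Life-year effect | QALY effect as planned | QALY effect with the true utility |
|---|---|---|---|
| No survival effect | −0.0002 | −0.0001 | 0.048 |
| 3-point mortality reduction | 0.0149 | 0.0122 | 0.061 |

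In the second row 0.0122 / 0.0149 = 0.82, about the assumed mean utility. The planned estimate recovers weighted survival and none of the utility benefit.

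**3. Size of the part that is kept.** Assumptions: utility 0.7 to 0.8, and deaths around day 15, so each averted death adds 350/365 of a year.

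- 1-point mortality difference: 0.01 × 350/365 = 0.0096 life-years. Times 0.7 to 0.8 this is 0.0067 to 0.0077 QALY, or £134 to £153 at £20,000 and £201 to £230 at £30,000.
- 5-point difference, utility 0.75: 0.05 × 350/365 × 0.75 = 0.0360 QALY, or about £719 at £20,000.

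**4. Size of the part that is left out.** QALY = utility difference × months / 12. The equivalent mortality difference divides this by 0.75 × 350/365 = 0.719. Utility differences and durations are assumptions.

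| Utility difference | Months | QALY | At £20,000 | At £30,000 | Equivalent mortality difference |
|---|---|---|---|---|---|
| 0.05 | 3 | 0.0125 | £250 | £375 | 1.7 points |
| 0.10 | 3 | 0.025 | £500 | £750 | 3.5 points |
| 0.10 | 6 | 0.05 | £1,000 | £1,500 | 7.0 points |

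Over a wider range, 0.02 for 1 month to 0.10 for 12 months, the omitted part runs from 0.0017 to 0.10 QALY: £33 to £2,000 at £20,000, and £50 to £3,000 at £30,000.

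**5. Break-even.** The net benefit changes sign when utility difference × months / 12 = ΔC / λ − u × ΔT. With ΔT = 0 and an assumed extra cost of £250 at λ = £20,000, the right-hand side is 0.0125 QALY, that is 0.05 for 3 months.

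**The case against.** The strongest reply has five parts.

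- **Utility might still vary.** The text does not say that the ICD-10 category is frozen at the index admission. All admissions over the following year are extracted, and an area-under-the-curve method allows for a changing score. This stands as a qualification. No updating is described, though, so the plan as written does not provide it.
- **The health effects are visible elsewhere.** Mortality, readmission, and days alive and out of hospital are main outcomes. Cost per life year is reported beside cost per QALY, and Objective 3 has a separate mortality criterion of 10% at one year. This is right, and a reader may therefore not infer that the study ignores these effects or cannot address cost-utility at all. The gap is in the QALY and in the main metric built on it.
- **Other utility sources are planned.** Literature values used in sensitivity analysis could differ by strategy, and a panel shown the scores could remark that they ignore treatment. Both are possible, but neither is stated as a purpose, and the base case would be unchanged.
- **The amounts are assumed.** They are. At the 5% difference named under Sample size, read as absolute mortality, the survival part (£719) exceeds both 3-month examples (£250 and £500), though not the 6-month one (£1,000).
- **Decrements in the base case would be a doubtful cure.** These conditions use the calculator because the review found no suitable values, and HES does not record continuing symptoms in patients never operated on. Decrements for recorded events alone could penalise surgery one-sidedly. This stands, and it is why the base case is left alone below.

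**Conclusion.** The point holds for conditions scored with the calculator, on the condition that utility is not updated after the index admission. Their incremental QALY is then survival weighted by a utility that does not depend on strategy. On the assumed inputs, the omitted part can be smaller or larger than the part retained, and it could favour either strategy.

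Three stronger readings are tempting but not supported. First, the QALY result is not a fixed multiple of the life-year result across patients, since utility varies with diagnosis, age and gender. Second, the protocol does not show that the intervals leave out all uncertainty about quality of life, because it does not say how that uncertainty is carried through. Third, it cannot be said that diverticulitis or hernia is affected, because the conditions are not named; hernia serves above only to show how strategies can differ.

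This is a cheap improvement. It does not invalidate the cost-effectiveness analysis, but it changes what the main metric can be said to show.

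**What to change.** Keep the calculator in the base case, and add the following to Objective 2 (Outcomes and Analysis), with a matching sentence in Objective 3, Analysis:

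- **(a) Sensitivity analysis.** Pre-specify time-limited utility decrements over stated ranges, tied to dated HES events already to be extracted: index stay, operation, emergency readmission, re-intervention, and the wait to delayed surgery. Include a range for continuing symptoms in patients not operated on, so that surgery is not penalised one-sidedly.
- **(b) Break-even.** For each such condition and subgroup, report the utility difference between strategies, with its duration, that would change the sign of the incremental net benefit at £20,000 and at £30,000 per QALY.
- **(c) Label.** Where utility does not differ by strategy, describe the QALY and net-benefit results as survival-driven, and do not classify a subgroup as cost-effective on them without the break-even result.

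The cost is protocol wording and a little more analysis. No new data are needed. The price is that the decrement ranges are assumptions and that conclusions for these conditions become less definite.

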1.1. Summary and objectives of the study

The aim of this 24-month study is to evaluate the effectiveness and cost-effectiveness of emergency surgery for common acute conditions such as appendicitis, that present as emergency admissions to NHS hospitals. The 'intervention' strategy is emergency surgery within the index hospital episode, and the 'comparator' strategy is non-operative care including: 'medical management', a 'non-surgical' procedure, and the possibility of subsequent planned (elective) surgery.

The specific objectives are to evaluate the:

1. effectiveness of emergency surgery versus non-operative care for common acute conditions presenting as emergency admissions across broad ICD-10 categories.
2. relative cost-effectiveness of emergency surgery versus non-operative care across broad ICD-10 categories.
3. clinical and cost-effectiveness of operative versus non-operative care for specific patient subgroups, including diagnostic subcategories and patient characteristics.

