Preparatory work to date has utilised emergency admission data for 2014-15 for a sample of half the acute NHS trusts in England. We used ICD-10 diagnosis codes to identify cohorts of emergency admissions, and an initial list of OPCS procedure codes to define relevant surgical procedures for these acute conditions. Table 1 lists the broad acute conditions, intervention and comparator strategies. The TTO estimates from the pilot data highlight that for each of these five acute conditions, there is wide variation in the proportion of patients who have emergency surgery across NHS trust hospitals.

Population

In the proposed study, the populations of interest will be defined by adult patients with an emergency admission to an NHS hospital in England between 1 April 2009 and 30 June 2020 for which one of the five eligible acute conditions is the primary reason for admission. Eligibility will be based on a final list of ICD-10 codes that specify that the acute condition is the 'main' diagnosis, and according to the findings of the first design workshop. For each patient, this admission then forms their *index admission*.

The exemplar, provisional 3-character ICD-10 codes for defining populations comprise: acute and unspecified appendicitis (K35, K37); cholelithiasis (K80); inguinal hernia (K40); diverticular disease of intestine (K57); vascular disorders of the intestine (K55). The final target populations for each condition will be defined with the expert clinical panel, taking place on 29 March 2020, which will determine the specific complications for inclusion related to each pathology.

Our initial analyses will also investigate pathways to diagnosis and to surgical or non-surgical care. This will help the research team and clinical panel refine the criteria for inclusion and exclusion, and for intervention or comparator. We will also examine inconsistencies between diagnoses and procedures and ensure the final definition of acute conditions ensure that for the cohort included they form the main reason for admission. This will involve: examination of diagnosis codes (specific codes and position in all episodes within an emergency admission); source of emergency admission (A&E, GP, inter-hospital transfer, etc); other potential diagnoses, e.g., other abdominal pain (R10); and multiple admissions for the same patient.

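### Objective 3 uses HES diagnosis as a baseline covariate and subgroup but does not limit it to what was known before the decision to operate, so the groups may depend on treatment

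*Protocol*

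**What the plan says.** Protocol section 1.1 makes the third objective an evaluation for "specific patient subgroups, including diagnostic subcategories and patient characteristics". Section 2.2.2, Objective 3, Design, aggregates individual effects over "relevant subgroups defined by risk factors such as refined diagnostic group, age, ethnicity" and other factors. It describes marginal patients by characteristics "measured in HES (e.g. age, comorbidity, diagnosis") and by unmeasured ones such as illness severity. Objective 3, Analysis, then models each patient's "propensity for emergency surgery according to their observed characteristics and the hospital TTO using a probit model", followed by outcome models on the same characteristics.

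Identification rests on a statement in the Design text: a small change in TTO can decide whether a marginal patient has surgery, "but will not change the distribution of their risk factors". The same text pictures two patients compared at the time of emergency admission.

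On the source of diagnosis codes, Objective 1, Population, bases eligibility on the main diagnosis, with final code lists left to the clinical panel. Its provisional list includes "acute and unspecified appendicitis (K35, K37"). Initial analyses will include "examination of diagnosis codes (specific codes and position in all episodes within an emergency admission"), in order to refine the inclusion, exclusion, intervention and comparator criteria. Note 1 to Table 1 lets a condition include its complications, also for the panel to settle. No section gives a code source or time point for the refined diagnostic group.

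**The concern.** A diagnosis coded in HES need not be a baseline characteristic. A perforation seen at operation may be coded, while the same perforation in a patient treated without surgery may not be. If so, the recorded group is partly a consequence of treatment.

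The instrument does not protect against this. A hospital with a higher TTO would move more truly complicated patients out of the uncomplicated code, leaving a milder mix there. Within that code TTO is then associated with prognosis, and the property on which Objective 3 relies fails. Adjusting for the code in the LIV models opens the same path.

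The results at stake are the diagnostic subgroup effects, which are meant to inform commissioners and guidelines. The uncomplicated groups are among those where surgery could wrongly appear protective.

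**Working it through.** The protocol gives no figure to reproduce here, so the mechanism was checked by exact expectations with the true effect of surgery set to zero.

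**Inputs from the document.** Table 1, appendicitis: quartiles of trust-level TTO 84.9% and 92.8%. These are pilot values; the primary analysis uses hospital-level TTO.

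**Assumed inputs.** 25% of patients are perforated. Mortality is 4% if perforated and 0.5% if not, whatever the treatment. Perforation is always recorded at operation, and in a share d of non-operated patients (d = 0.3, 0.5, 0.7). Perforated and non-perforated patients are operated on at the same rate.

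**Formulas for the group recorded as uncomplicated**, at TTO = T:
- missed perforations m = 0.25 × (1 − T) × (1 − d)
- group size N = 0.75 + m
- mortality Y = (0.75 × 0.005 + m × 0.04) / N
- operated share D = 0.75 × T / N
- IV (Wald) estimate = difference in Y / difference in D

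**Worked case, d = 0.5.**
- T = 0.849: m = 0.018875, N = 0.768875, Y = 0.004505 / 0.768875 = 0.5859%, D = 0.63675 / 0.768875 = 0.8282.
- T = 0.928: m = 0.009, N = 0.759, Y = 0.00411 / 0.759 = 0.5415%, D = 0.696 / 0.759 = 0.9170.
- Estimate = (0.5415 − 0.5859) / (0.9170 − 0.8282) = −0.50 percentage points.

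**If operation varies with severity.** Let perforated patients go unoperated at k times the rate u of the others, with overall TTO held at the same two values, so that u × (0.75 + 0.25k) = 1 − T. In the formulas m becomes 0.25 × k × u × (1 − d), and the numerator of D becomes 0.75 × (1 − u). Estimates in percentage points:

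| k | d = 0.3 | d = 0.5 | d = 0.7 | d = 1 |
|---|---|---|---|---|
| 1 | −0.66 | −0.50 | −0.32 | 0 |
| 0.5 | −0.37 | −0.27 | −0.17 | 0 |
| 0.25 | −0.19 | −0.14 | −0.09 | 0 |

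If the non-operation rate among perforated patients does not change with TTO, m is the same at both quartiles and the estimate is zero.

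**Relative size, k = 1.** Non-operated mortality in the group is (0.00375 + 0.25 × (1 − d) × 0.04) / (0.75 + 0.25 × (1 − d)) = 1.16%, 1.00% and 0.82% for d = 0.3, 0.5 and 0.7. Operated mortality is 0.5%. The apparent reductions are 57%, 50% and 39%.

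**Second check, other assumed inputs.** 25% complicated; mortality 10% against 2%; complication recorded in 95% of operated patients and in 80%, 60% or 40% of non-operated patients; TTO quartiles of each of the five conditions.
- Without conditioning on diagnosis: 0.00 points throughout.
- Recorded uncomplicated group: −0.37, −0.81, −1.20 points for every condition.
- Recorded complicated group: 0.00 points. It becomes +1.60 if recording is 60% and 5% of uncomplicated non-operated patients are also coded as complicated.
- Two-stage least squares with recorded diagnosis as a covariate, no false positives: −0.28 to −1.07 points overall.
- Recording 95% in both treatment groups: 0.00 points everywhere.

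These are linear IV calculations. They show the direction and rough size of the problem, not the output of the LIV probit models.

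**The case against.** A reader might infer that Objective 3 takes diagnoses from the whole admission, operative findings included. The document does not support this. The phrase "specific codes and position in all episodes within an emergency admission" describes exploratory work on eligibility and strategy definitions. The one covariate window that expressly includes the index admission, in the case-mix section, is for comorbidity. A spurious effect is therefore possible but not established.

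It is also fair to say that code lists are openly deferred to the clinical panel and later analysis plans, and that detail of that kind is not a defect in a protocol. K35 and K37 are listed as one provisional population, and no section splits them. The section on checking IV assumptions already promises to explore covariate balance across TTO in the full data.

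Part of this stands, but it does not dispose of the point. The protocol itself classes diagnosis as a measured prognostic factor and asserts that TTO leaves the distribution of risk factors unchanged. Treatment-dependent recording would break that assertion, whatever codes the panel chooses. The balance check does not name diagnosis, its reported pilot result is at trust level, and no response to imbalance is given.

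On size, a reader might take from the illustration that a null effect would read as surgery preventing more than half of deaths. Against non-operated mortality that holds in only one of the three equal-rate scenarios. The artefact shrinks further if severe cases are more likely to be operated on, which fits the protocol's own premise that operated patients may be sicker.

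Dropping or pooling severity codes outright would lose prognostic information and curtail a stated objective, so it is not the obvious remedy.

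**Conclusion.** The point holds as a conditional weakness of Objective 3. Diagnosis and refined diagnostic group serve as baseline covariates and subgroups with no restriction to information that precedes the decision to operate. Where recording depends on having surgery, the LIV assumption about risk factors fails, and a null effect can appear as a non-zero one.

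Under the appendicitis inputs the artefact is about −0.1 to −0.7 percentage points in the recorded uncomplicated group. It is zero if recording does not depend on surgery, or if non-operation of severe cases does not vary with TTO. Only the TTO quartiles come from the protocol; the severity, mortality and recording inputs are assumed. The second set of inputs gives up to −1.20 points in the same kind of group, so the size is not settled.

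All of this is far below the 10% difference in one-year mortality that Objective 3 sets as the clinical benefit of interest. It can still matter, because the protocol also reports mean differences with 95% confidence intervals and judges cost-effectiveness by a positive incremental net benefit with no margin. With an estimated 333,000 appendicitis admissions, a small bias could look precise. IV analyses that do not condition on refined diagnosis are not affected by this route.

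**What to change.** 1. In Objective 3, define refined diagnostic groups from information that precedes surgery, where HES allows it, and state the code source and time point.
2. Name refined diagnostic group in the planned assessment of covariate balance, and regress each group's hospital-year share on hospital-level TTO.
3. Repeat the LIV analysis without refined diagnosis as a covariate, and report both sets of results.
4. Where a group's share moves with TTO, report that subgroup's effect as descriptive, noting that true case-mix differences between hospitals could also explain the shift; the regression cannot separate the two.

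The cost is some wording, one extra table and one extra model run on data the study will already hold. The downside is that some diagnostic subgroup results carry a weaker claim.
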